Appendix 1a Schedule of Activities (cont.)

Hospitalized Days (only to be completed while patients are hospitalized)																						
	D -2,-1	D1 (Randomization)	D2	D3	D4	D5	D6	D7	D8	D9	D10	D11-13	D14	D15-19	D20	D21-24	D25	D26-29	D30	Hospital Discharge ^a	D60 Study Completion or Early Discontinuation while hospitalized	Unscheduled
██████████		x	x	x	x	x	x	x	x	x	x		x		x		x		x	x	x	(x)
██████████		x	x	x	x	x	x	x	x	x	x		x		x		x		x	x	x	(x)
Flu antibodies (HAI) ^x		x											x						x	x	x	(x)
██████████		x																	x	x	x	(x)
Serum for MHAA4549A PK measurements ^y		x	x	x		x		x					x						x	x	x	(x)
██████████		x				x														(x)		(x)

Appendix 1a Schedule of Activities (cont.)

Hospitalized Days (only to be completed while patients are hospitalized)																						
	D -2,-1	D1 (Randomization)	D2	D3	D4	D5	D6	D7	D8	D9	D10	D11-13	D14	D15-19	D20	D21-24	D25	D26-29	D30	Hospital Discharge ^a	D60 Study Completion or Early Discontinuation while hospitalized	Unscheduled
██████████																				aa		
██████████ ██████████ ██████████ ██████████		x	x	x		x		x			x		x		x		x		x	x	x	(x)
██████████ ██████████ ██████████		x	x	x		x		x			x		x		x		x		x	x	x	(x)
██████████		x																	x	x	x	(x)
██████████		x																	x	x	x	(x)
██████████ ██████████		x																	x	x	x	(x)
██████████ ██████████																				x		

Appendix 1a Schedule of Activities (cont.)

Hospitalized Days (only to be completed while patients are hospitalized)																						
	D -2,-1	D1 (Randomization)	D2	D3	D4	D5	D6	D7	D8	D9	D10	D11-13	D14	D15-19	D20	D21-24	D25	D26-29	D30	Hospital Discharge ^a	D60 Study Completion or Early Discontinuation while hospitalized	Unscheduled
Oseltamivir medication diary ^{dd}																				x		
Clinical status assessment ^{ee}		x	x	x	x	x	x	x					x						x			

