6.4 EFFICACY ANALYSES

The primary and secondary efficacy analyses will include all randomized patients who are confirmed to be influenza A infected, with patients grouped according to the treatment assigned at randomization.

Time to event data will be *analyzed* using Kaplan-Meier methodology and stratified Cox proportional hazards models and will be summarized using n, median when estimable, hazard ratios, and 95% confidence intervals. Patients who are lost to follow-up (while event free) will be censored at the time that they are last known to be event free.

The ordinal outcomes will be analyzed using a proportional odds model. To supplement the overall summary odds ratio, separate odds ratios will be estimated for each dichotomized definition of improvement that can be formulated from the components of the ordinal outcome. A test for the proportionality assumption will also be made. Patients discharged from the hospital to a rehabilitation facility will be included in category 5. Patients discharged from the hospital to a nursing home will also be included in category 5, unless the patient lived in a nursing home prior to admission to the hospital, in which case the patient will be characterized based on resumption of normal activities.

Estimation of the treatment difference of proportions and *the corresponding* 95% confidence intervals will be calculated using stratum-adjusted Mantel-Haenszel methodology (Koch et al. 1989). For continuous endpoints, Analysis of Covariance methods (after appropriate transformation of data) will be used to estimate treatment differences and 95% confidence intervals.

Other than censoring in the time to event analyses, no other imputation for missing data will be performed.

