Appendix 1a Schedule of *Activities*

Notes: Unless otherwise indicated, **all assessments on Day 1 should be performed prior to study drug administration**; x's within parentheses, i.e., (x), indicate optional assessments. Please refer to Follow-up Period table for visits to be completed after patient is discharged from hospital prior to Day 60. Any screening assessments completed prior to consent as standard of care do not need to be repeated if done within the screening period. If a patient is unable to be present at the site for a follow-up visit, a telephone visit is *encouraged*.

Hospitalized Days (only to be completed while patients are hospitalized)																						
	D -2,-1	D1 (Randomization)	D2	D3	D4	D5	D6	D7	D8	D9	D10	D11-13	D14	D15-19	D20	D21-24	D25	D26-29	D30	Hospital Discharge ^a	D60 Study Completion or Early Discontinuation while hospitalized	Unscheduled
Informed consent ^b	x																					
Sponsor-approved influenza test ^c	x																					
Inclusion/exclusion criteria	x																					
Medical history and demographic	x																					

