Appendix 1a Schedule of Activities (cont.)

[REDACTED]; AE=adverse event; APACHE=Acute Physiology and Chronic Health Evaluation; ATA=Anti-therapeutic antibodies; D=day; Dx=diagnostics; eCRF=electronic Case Report Form; ECG=electrocardiogram; HAI=hemagglutinin inhibition; [REDACTED]; ICU=Intensive Care Unit; IRB/IEC=Independent Review Board/Independent Ethics Committee; NAI=neuraminidase inhibitor; O₂=oxygen; PaO₂/FiO₂=partial pressure of oxygen/fraction of inspired oxygen; PCR=polymerase chain reaction; PD=pharmacodynamics; PK=pharmacokinetic; PPV=positive pressure ventilation; qPCR=quantitative Polymerase Chain Reaction; RBCs=red blood cells; SOFA=Sequential Organ Failure Assessment; SpO₂=oxygen saturation measured by pulse oximetry; WBCs=white blood cells.

- ^a Assessments to be performed irrespective of day of discharge. Assessments on discharge day will supersede assessments for matching day except for the study completion/early discontinuation visit (e.g., If a patient is discharged from the hospital on Day X, use assessments under “hospital discharge” column instead of the Day X column and record under the hospital discharge folder in the eCRF. If a patient discontinues from the study early on Day X, complete all assessments under the “early discontinuation” column and record under the early discontinuation folder in the eCRF.
- ^b Informed consent must be obtained from all patients. For patients who are unable to consent, an authorized representative may be used if allowed by local regulations and IRB/IEC policy.
- ^c Sponsor-approved influenza test using a nasopharyngeal swab in one nostril *or lower respiratory tract sample (if appropriate for the sponsor-approved local PCR test)*. A Sponsor-approved influenza test includes influenza antigen test or influenza polymerase chain reaction (PCR) test. Result must be available within the 48-hour screening window.
- ^d A urine *or serum* pregnancy test should be collected only for women considered by the investigator to be of childbearing potential, see exclusion criteria. This result must be available within 2 days prior to study treatment. If urine testing is not available at the site, blood already collected from an existing sample may be tested for pregnancy.
- ^e Confirm patient requires supplemental O₂ or PPV within 24 hours of hospital admission.

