Appendix 1b Schedule of *Activities*: Follow-Up Period

- If a patient is discharged prior to Day 14, he/she will need to complete the following assessments for Day 14, Day 30, and Day 60 below.
- If a patient is discharged after Day 14 but prior to Day 30, he/she will need to complete the following assessments for Day 30 and Day 60 below.
- If a patient is discharged after Day 30, but prior to Day 60, he/she will need to complete the following assessments for Day 60 below.
- If patient is hospitalized for Day 14, Day 30, and/or Day 60, please refer to Appendix 1a.

Day (D)	D14 ± 1 (If discharged BEFORE Day 14)	D30 ± 4 (If discharged BEFORE Day 30)	Day 60 ± 7 (Study Completion) or Early Discontinuation
Concomitant medications ^a	x	x	x
Vital signs ^b	x	x	x
Electrocardiogram (12-lead) ^c	x	x	x
Weight, BMI ^d	x	x	x
Adverse events	x	x	x
Hematology ^e	x	x	x
Chemistry panel ^e	x	x	x
Coagulation panel ^e	x	x	x
Urinalysis ^e	x	x	x
Flu antibodies (HAI)	x	x	x
[REDACTED]		x	x
Serum for MHAA4549A PK measurements ^f	x	x	x
[REDACTED]	x	x	x
[REDACTED]	x	x	x
[REDACTED]		x	x
[REDACTED]		x	x
[REDACTED]		x	x

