Appendix 1b Schedule of Activities: Follow-Up Period (cont.)

Day (D)	D14 ± 1 (If discharged BEFORE Day 14)	D30 ± 4 (If discharged BEFORE Day 30)	Day 60 ± 7 (Study Completion) or Early Discontinuation
[REDACTED]		x	x
Clinical status assessment^h	x	x	

[REDACTED]; ATA = Anti-therapeutic antibodies; BMI = body mass index; D = day;
 Dx = diagnostics; eCRF = electronic Case Report Form; ECG = electrocardiogram; HAI = hemagglutinin inhibition; [REDACTED]
 [REDACTED] PD = pharmacodynamics; PK = pharmacokinetic.

- ^a Concomitant medications should be recorded for 30 days prior to screening, through the study completion/early discontinuation visit. See exclusion criteria in [Section 4.1.2](#) for prohibited therapies.
- ^b Vital signs include temperature, respiratory rate, heart rate, systolic blood pressure, and diastolic blood pressure. Temperature should be measured using the same methodology throughout the study and should be measured prior to study drug administration of any antipyretic drugs. In patients who have multiple vital signs taken during any day, the most abnormal value should be recorded from that 24-hour period. Temperature, blood pressure, respiratory rate, and heart rate will be completed after the patient has been in a seated or supine position for > 5 minutes.
- ^c ECG should be recorded after the patient has rested in a supine position for 10 minutes.
- ^d Weight will be recorded in kg.
- ^e Local laboratory measurements should be used.
- ^f PK samples must be labeled with the exact time of draw.

^h Indicate which clinical status the patient is categorized under: death; in the ICU; non-ICU hospitalization, requiring supplemental oxygen; non-ICU hospitalization, not requiring supplemental oxygen; not hospitalized, but unable to resume normal activities; or not hospitalized with full resumption of normal activities

Appendix 2

Time to Normalization of Respiratory Function

For the purposes of this study, the time to normalization of respiratory function will be defined as the time to removal of the patient from O₂ supplementation in order to maintain an SpO₂ ≥95%.

*Unless clinically contraindicated**, patients who are on low flow O₂ (i.e., 2-6 L/min) should receive a daily trial off O₂ in the morning between 6:00 a.m. and 12:00 noon as described below.

1. Patient should be resting or sitting.

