Appendix 12 ***Clinical Status Assessment***

Clinical status will be assessed on Days 1-7, 14, and 30. Assessment should be collected at a consistent time throughout the study. Indicate the patient's clinical status for the day:

- 1. Death;*
- 2. In the ICU;*
- 3. Non-ICU hospitalization, requiring supplemental oxygen;*
- 4. Non-ICU hospitalization, not requiring supplemental oxygen;*
- 5. Not hospitalized, but unable to resume normal activities; or*
- 6. Not hospitalized with full resumption of normal activities*

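### The Version 7 schedule has no collection point for the ordinal clinical status of patients discharged on Days 2–7, although the endpoint is defined for all patients on those days

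*Combined protocol and SAP*

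**What the plan says.** Sections 2.3 and 3.3.3 of the Version 7 protocol define a six-category ordinal status on Days 1–7, 14 and 30. Category 1 is death, 2 to 4 are inpatient states, and 5 and 6 are patients out of hospital without and with full return to normal activities. Appendix 12 repeats the days without any hospitalization condition: "Clinical status will be assessed on Days 1-7, 14, and 30".

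The schedules say something narrower.

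- Appendix 1a marks the item on Days 1–7, 14 and 30, under columns headed "Hospitalized Days (only to be completed while patients are hospitalized". The Hospital Discharge, Day 60/Early Discontinuation and Unscheduled columns are blank for this row.
- Footnote a of Appendix 1a makes the discharge column replace that day's column: "Assessments on discharge day will supersede assessments for matching day except for the study completion/early discontinuation visit".
- Under Appendix 1b, for a patient who leaves before Day 14, "he/she will need to complete the following assessments for Day 14, Day 30, and Day 60 below". Clinical status is marked there at Days 14 and 30 only.

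Section 6.4 analyses ordinal outcomes with a proportional odds model in all randomized patients with confirmed influenza A. It places discharges to a rehabilitation facility, and to a nursing home where the patient did not live before, in category 5. It ends: "Other than censoring in the time to event analyses, no other imputation for missing data will be performed".

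**The concern.** If sites follow the schedule, the record stops when the patient goes home. Going home early is what categories 5 and 6 exist to capture, so the missing values would be concentrated in the best outcomes, and more of them would fall in whichever arm recovers faster. A daily model fitted only to patients with a recorded status would compare groups selected after randomization for still being ill.

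The Version 7 amendment rationale gives the expected gain in power over a binary outcome as the reason for adding this endpoint. That gain depends on the full scale being observed. The split between categories 5 and 6 also cannot be reconstructed later unless someone asks the patient.

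**Working it through.** The plan states no sample size or power for this endpoint, so there is no figure to reproduce. The check is a reading of the schedule, followed by two illustrations whose inputs are assumptions.

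**1. Tracing a discharge.** Appendix 1a, footnote m, keeps patients in hospital for at least 24 hours after infusion, so discharge is possible from Day 2. Take a patient sent home on Day 4.

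- Days 1–3: status recorded (Appendix 1a).
- Day 4: the discharge column replaces the Day 4 column and has no status mark, so nothing is scheduled.
- Days 5–7: the Appendix 1a columns no longer apply, and Appendix 1b has no contact before Day 14.
- Days 14 and 30: status recorded (Appendix 1b).

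The endpoint is therefore unscheduled on Days 4–7 for this patient. Across all patients, categories 5 and 6 have no collection point on Days 2–7, which are six of the nine listed days. Section 6.4 gives no rule for a patient discharged home without a record.

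**2. How many patients (illustration).** Section 1.1 cites hospital stays of 5–9 days. Assume that range is a median, counted from Day 1, with exponential times. The share discharged by day d is 1 − 2^(−d/median).

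| Median stay | By Day 3 | By Day 5 | By Day 7 | Day 7, of 330 |
|---|---|---|---|---|
| 5 days | 34% | 50% | 62% | about 205 |
| 7 days | 26% | 39% | 50% | about 165 |
| 9 days | 21% | 32% | 42% | about 138 |

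For example, 1 − 2^(−7/5) = 0.621 and 1 − 2^(−7/9) = 0.417. The 330 is the planned enrollment in Section 6.1. Allowing for the 24-hour stay, 1 − 2^(−(d−1)/(median−1)) gives 65%, 50% and 41% by Day 7.

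**3. Direction of bias if these patients drop out (illustration).** Section 3.2.2 cites 27% needing ICU admission. Assume those patients stay in ICU all week in both arms, and that the drug only shortens non-ICU discharge, from a median of 5 days to 4.

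- The non-ICU share still in hospital on day d is 0.73 × 2^(−d/5) in control and 0.73 × 2^(−d/4) in active.
- Among inpatients, the odds ratio for better status (not in ICU) is the ratio of these two, 2^(−d/20). This is 0.841 on Day 5 and 0.785 on Day 7.
- With everyone classified, the discharged share on Day 5 is 0.365 in control and 0.423 in active. The odds ratio is (0.423/0.577)/(0.365/0.635) = 1.28.
- On Day 7 the shares are 0.453 and 0.513, and the odds ratio is 1.27.

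Under these assumptions a real benefit appears as harm among inpatients. A drug that also helped ICU patients would show less distortion.

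**4. Day 1.** The notes to Appendix 1a say that, unless otherwise indicated, "all assessments on Day 1 should be performed prior to study drug administration". The footnote to the clinical-status row gives no exception, so Day 1 status is a baseline value.

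**The case against.** A reader might infer that the plan intends an inpatient-only analysis on each of Days 2–7. The documents do not support that. Section 6.4 analyses all randomized confirmed-infected patients and assigns some discharged patients to category 5. Section 6.4.2 asks for the proportion in each of the six categories on every listed day. The footnote to the Appendix 1a row itself lists death and both out-of-hospital categories. The heading over the columns is generic to the whole table. What exists is a conflict between schedule and definition.

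It can also be said that little is truly lost. Discharge is recorded in its own eCRF folder, and duration of hospitalization, readmission and mortality are separate endpoints, so the relevant dates are needed anyway. Placing a living, discharged patient in a not-hospitalized category is derivation from recorded facts, which the no-imputation sentence does not clearly forbid. Section 6 defers further analysis detail to a separate SAP, and no text of it appears in the documents reviewed, so a rule may exist there.

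These points stand, and they limit the claim. They do not remove it. The visible text states no derivation rule for home discharges, and no date can separate category 5 from category 6. The nursing-home provision in Section 6.4 also depends, for returning residents, on resumption of normal activities, which is not collected after discharge on Days 2–7.

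Finally, this is one of many secondary endpoints in a study whose Section 6 states that no formal hypothesis testing will be done. That bears on severity, not on whether the conflict exists.

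**Conclusion.** The conflict is established from the Version 7 text. As scheduled, and with no imputation, patients discharged home on Days 2–7 have no status record from the discharge day through Day 7. Missingness is then tied to good outcome, and the category 5 versus 6 split is unobserved on those days.

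The effect on the analysis is conditional. If such patients drop out of the daily models, the treatment effect is diluted and could reverse. The 42–62% discharged by Day 7 assumes an exponential stay with a median of 5–9 days. The reversal in the illustration further assumes a fixed ICU group and a drug effect on non-ICU discharge only. It shows that reversal is possible; the documents do not show that it is likely.

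Days 14 and 30 are collected in and out of hospital, deaths and some facility discharges have a stated category, and the primary endpoint is untouched. This should be fixed, at the level due to a secondary endpoint. Listing Day 1 as an outcome day is a minor point.

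**What to change.** Preferred: add the clinical-status mark to the Hospital Discharge column of Appendix 1a, and in Appendix 1b collect Days 2–7 status for discharged patients by phone or by recall at the Day 14 visit. This brings the schedule into line with Appendix 12. It costs a short schedule amendment and a brief contact or a few recall questions, with some recall error.

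Without an amendment: state in the SAP that on Days 2–7 a living patient who has been discharged and not readmitted is in a merged category 5/6 from the discharge date, and that a patient who has died is in category 1 from the death date. No discharged patient is then missing. A readmitted patient would return to the applicable inpatient category. This takes one paragraph and uses dates already needed for other endpoints. The downside is that categories 5 and 6 cannot be separated before Day 14, so the Days 2–7 models have five levels.

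In either case, report Day 1 status as baseline and use it as a covariate in the proportional odds models rather than as an outcome day.

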Appendix 1a Schedule of Activities (cont.)

[REDACTED]; AE=adverse event; APACHE=Acute Physiology and Chronic Health Evaluation; ATA=Anti-therapeutic antibodies; D=day; Dx=diagnostics; eCRF=electronic Case Report Form; ECG=electrocardiogram; HAI=hemagglutinin inhibition; [REDACTED]; ICU=Intensive Care Unit; IRB/IEC=Independent Review Board/Independent Ethics Committee; NAI=neuraminidase inhibitor; O₂=oxygen; PaO₂/FiO₂=partial pressure of oxygen/fraction of inspired oxygen; PCR=polymerase chain reaction; PD=pharmacodynamics; PK=pharmacokinetic; PPV=positive pressure ventilation; qPCR=quantitative Polymerase Chain Reaction; RBCs=red blood cells; SOFA=Sequential Organ Failure Assessment; SpO₂=oxygen saturation measured by pulse oximetry; WBCs=white blood cells.

- ^a Assessments to be performed irrespective of day of discharge. Assessments on discharge day will supersede assessments for matching day except for the study completion/early discontinuation visit (e.g., If a patient is discharged from the hospital on Day X, use assessments under “hospital discharge” column instead of the Day X column and record under the hospital discharge folder in the eCRF. If a patient discontinues from the study early on Day X, complete all assessments under the “early discontinuation” column and record under the early discontinuation folder in the eCRF.
- ^b Informed consent must be obtained from all patients. For patients who are unable to consent, an authorized representative may be used if allowed by local regulations and IRB/IEC policy.
- ^c Sponsor-approved influenza test using a nasopharyngeal swab in one nostril *or lower respiratory tract sample (if appropriate for the sponsor-approved local PCR test)*. A Sponsor-approved influenza test includes influenza antigen test or influenza polymerase chain reaction (PCR) test. Result must be available within the 48-hour screening window.
- ^d A urine *or serum* pregnancy test should be collected only for women considered by the investigator to be of childbearing potential, see exclusion criteria. This result must be available within 2 days prior to study treatment. If urine testing is not available at the site, blood already collected from an existing sample may be tested for pregnancy.
- ^e Confirm patient requires supplemental O₂ or PPV within 24 hours of hospital admission.
- ^f *Unless clinically contraindicated, all* patients will have their on-study SpO₂ and corresponding respiratory assessments recorded daily in the morning between 6:00 a.m. and 12:00 noon local time; screening SpO₂ may be taken outside this window. From Day 1 onward post-study drug administration, patients on low flow O₂ should have a daily trial of their SpO₂ while on and off the supplementation and both values will be recorded. If the patient is on oxygen supplementation, SpO₂ measured by pulse oximetry and the corresponding respiratory assessments (e.g., FiO₂, flow rate) will be recorded. If the patient is on PPV, PaO₂ and the corresponding respiratory assessments (e.g., FiO₂, ventilator mode, ventilator respiratory rate, positive end-expiratory pressure) will be recorded. If clinically appropriate (i.e., the patient is on non-invasive PPV), the conversion table in Appendix 11 may be used.
- ^g Concomitant medications should be recorded for 30 days prior to screening, through the study completion/early discontinuation visit. See exclusion criteria in [Section 4.5.2](#) for prohibited therapies.

Appendix 1a Schedule of Activities (cont.)

- ^h Vital signs will be collected within 1 hour before MHAA4549A infusion and within 1 hour after completion of MHAA4549A infusion and include temperature, respiratory rate, heart rate, systolic blood pressure, and diastolic blood pressure. Temperature should be measured using the same methodology throughout the study and should be measured prior to administration of any antipyretic drugs. In patients who have multiple vital signs taken during any day, the most abnormal value should be recorded from that 24-hour period. Temperature, blood pressure, respiratory rate, and heart rate will be completed after the patient has been in a seated or supine position for > 5 minutes. The worst/most abnormal value from the last 24-hour period should be recorded for patients who are in the ICU.
- ⁱ APACHE scores are optional and only for patients that are in the ICU. For calculation of the screening APACHE score, the worst values in the *first* 24 hours should be used. APACHE scores are not required for study conduct or entry but should be collected if available.
- ^j Assessment to be conducted based on entry into ICU; may vary from patient to patient.
- ^k SOFA scores are *optional and* only for patients in the ICU that have available data such as PaO₂/FiO₂ (mmHg). See Appendix 7 for SOFA score calculation.
- ^l Patient should rest in a supine position for 10 minutes prior.
- ^m Patient will be a resident for at least 24 hours following administration of MHAA4549A.
- ⁿ Oseltamivir must be given for a minimum of 5 days. Treatment longer than 5 days is permitted based on the discretion of the investigator [indicated by (x)].
- ^o Complete physical examination includes evaluations of general appearance of head, eyes, ears, nose, and throat, cardiovascular, dermatological, musculoskeletal, respiratory, gastrointestinal, genitourinary, and neurological systems. Changes from any prior examination should be recorded. New or worsened abnormalities should be recorded as AEs, if appropriate. Day 1 physical examination is optional if *already completed* on Day -1 or -2.
- ^p Limited, symptom-directed physical examination includes, at a minimum, evaluation of general appearance, dermatological examination of the injection sites, evaluations directed by patient-reported symptoms, and any other evaluations that the investigator deems clinically relevant. Changes from any prior examination should be recorded. New or worsened abnormalities should be recorded as AEs, if appropriate.
- ^q Height will be obtained at screening only. Weight will be obtained at all indicated visits. Height and weight will be recorded in centimeters and kilograms, respectively.
- ^r Local laboratory measurements should be utilized.
- ^s For optional thyroid stimulating hormone test.
- ^t Urinalysis includes pH, specific gravity, glucose, protein, ketones, blood, bilirubin, nitrite, and leukocyte esterase. Microscopic examination (e.g., sediment, RBCs, WBCs, casts, crystals, epithelial cells, bacteria) will be performed if clinically indicated.
- ^u HIV serology result not needed for randomization and a positive result does not require patient discontinuation.

